5.10.2 Primary bleeding endpoint

The primary bleeding endpoint is *major bleeding*, defined by one or more of the events defined by ISTH.

- All major bleeds must be symptomatic or clinically-overt [33].
- Bleeding that is asymptomatic, such as a small retroperitoneal bleed identified as an incidental finding on computed tomography, would not qualify as a major bleed.
- Similarly, intra-operative bleeding that is expected due to the type of surgical procedure and requires blood transfusion of ≥2 units packed red blood cells would not qualify as a major bleed.
- Furthermore, intra-operative fluid administration that is associated with a decrease in hemoglobin level >20 g/L (>2 g/dL), due to hemodilution, would not qualify as a major bleed.

1) symptomatic or clinically-overt bleeding that is associated with one or more of:

- > transfusion of ≥ 2 units heterologous packed red blood cells or whole blood
- > decrease in hemoglobin level >20 g/L (>2 g/dL).

CONFIDENTIAL

- need for re-operation or invasive intervention (*e.g.*, evacuation of wound hematoma)
- 2) symptomatic or clinically-overt bleeding at a critical anatomic site
 - bleeding that is intracranial, intraspinal, intraocular, retroperitoneal, intraarticular, pericardial, or intramuscular with compartment syndrome
- 3) *fatal bleeding*
 - bleeding that directly contributes to death (*e.g.*, intracranial bleed) or causes clinical deterioration leading to death (*e.g.*, bleed associated with sepsis or major organ failure)

5.10.3 Secondary efficacy endpoints

1) Acute myocardial infarction (ST- and non-ST-elevation) [34]

- typical rise and gradual fall (cardiac troponin) or more rapid rise and fall (creatine kinase-MB) of biochemical markers of myocardial necrosis to at least twice the upper limit of the normal range, with at least one of the following:
 - ischemic symptoms
 - development of pathologic Q-waves on the electrocardiogram (ECG)
 - ECG changes indicative of ischemia (*e.g.*, ST-segment elevation or depression)
 - > coronary artery intervention (*e.g.*, coronary angioplasty)
- 2) Deep vein thrombosis (both criteria must be satisfied) [35, 36]:
 - symptomatic venous thrombosis (lower or upper limb deep veins, or intraabdominal veins)
 - verified by non-compressibility on venous ultrasound or intraluminal filling defect on venography

3) Pulmonary embolism (both criteria must be satisfied) [37]:

- symptoms of thrombosis of the pulmonary arteries
- verified by high-probability ventilation-perfusion lung scan or intraluminal filling defect on CT angiography, or intraluminal filling defect pulmonary angiography or a non-diagnostic ventilation-perfusion lung scan with positive testing for deep vein thrombosis as defined above

4) Death

death of any cause based on autopsy findings or other medical records.

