5.2.2 Exclusion criteria

One or more of the following criteria precludes trial eligibility:

- any mechanical prosthetic heart valve
- stroke (ischemic or hemorrhagic), systemic embolism or TIA within past 12 weeks
- venous thromobembolism (deep vein thrombosis and/or pulmonary embolism) within past 12 weeks
- major bleeding within past 6 weeks
- severe renal insufficiency (calculated creatinine clearance <30 mL/min by Cockcroft-Gault equation)*
- thrombocytopenia (platelet count $<100 \times 10^{9}/L$)*
- life expectancy <1 month
- condition that impairs compliance with trial protocol (e.g., cognitive impairment, uncontrolled psychiatric condition, geographic inaccessibility)
- pregnancy
- allergy to heparin or history of heparin-induced thrombocytopenia
- patient is having one of the following surgeries/procedures during warfarin interruption:

 (a) cardiac surgery (*e.g.*, coronary artery bypass, heart valve replacement);
 (b) neurosurgery that is intracranial or intraspinal (*e.g.*, tumor resection, aneurysm repair);
 (c) high-risk non-surgical procedures (*e.g.*, brain biopsy)
- other surgical or non-surgical procedure that, at the discretion of the surgeon or proceduralist, precludes administration of therapeutic-dose LMWH at any time in the post-procedure period
- more than one surgery planned during the trial period
- prior participation in this trial

*The BRIDGE trial mandates that within 90 days prior to the planned surgery/procedure, study patients have had the following laboratory tests done to allow an assessment of patient eligibility for the trial: complete blood count (CBC), to include platelet count; serum creatinine.

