5.3.1 Minor surgery/procedure

- gastrointestinal endoscopy (with or without biopsy)
- cardiac catheterization (with or without percutaneous coronary intervention)
- dental surgery or other dental procedure
- dermatologic surgery or other dermatologic procedure
- cataract removal or other ophthalmologic procedure
- any other surgery or procedure lasting <1 hour

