5.12 Statistical Analysis of Endpoints

The analysis of study endpoints is based on events which occurred between the day of warfarin discontinuation (Day -5) and 30 to 37 days after the day of the surgery/procedure (Day +30 to Day +37).

If a patient has the surgery/procedure delayed for ≤ 3 days, the final day of follow-up will be 30 to 37 days after the rescheduled surgery/procedure date (i.e., Day +30 to +37 after new Day 0). If a patient has the surgery/procedure delayed for >3 days or cancelled and study drug is no longer administered, the final day of follow-up will be 30 to 37 days after the originally scheduled surgery/procedure date (i.e., Day +30 to +37 after original Day 0). If follow-up data is not available for the specified time points and the patient is alive, the patient will be considered missing for the primary endpoints.

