7.0 Potential Co-Interventions

7.1 Concomitant Antiplatelet Therapy

A considerable proportion of patients who are screened for this trial use concomitant antiplatelet therapy with warfarin. For example, low-dose aspirin (\leq 100 mg per day) is used by approximately 25% of patients with chronic atrial fibrillation who, typically, have concomitant coronary artery disease or other arterial vascular disease [38]. Antiplatelet drugs are also standard of care for some procedures, such as percutaneous coronary interventions, and mandating interruption of antiplatelet therapy in these settings would make the Trial results less applicable to "real world" clinical practice. Specifying separate protocols for periprocedural interruption of aspirin, clopidogrel and/or other antiplatelet drugs would also add complexity, impair study feasibility, and increase the potential for protocol violations.

Power calculations usually assume that events occur homogeneously across an entire group (either treated or placebo). However, it is possible that patients on aspirin or other antiplatelet drugs could have higher expected bleeding rates than the rest of the study population. Although these patients will be randomized to bridging anticoagulation or placebo, the potential exists for the antiplatelet subjects to be assigned unequally between the two arms by play of chance. To address this concern, we have conducted statistical simulations of the effect of antiplatelet therapy on the proposed trial design, demonstrating that concomitant antiplatelet therapy will not significantly alter the statistical power of the trial or its alpha level Consequently, for this trial, *the management of perioperative antiplatelet drug therapy will be left to the discretion of the treating clinician*.

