9.6 Clinical Event Classification (CEC) Committee

The CEC Committee will be an independent committee with no direct involvement in the day-today undertaking of the trial. The overall responsibility of the CEC Committee is to provide an independent and blinded adjudication of the primary efficacy and safety outcomes as well as all cause deaths.

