11.1 Serious Adverse Events

A Serious Adverse Event (SAE) is any adverse event that, at any dose:

Results in death.

- Is life threatening
 - > The term "life-threatening" in the definition of "serious" refers to an event in which the subject was at risk of death at the time of the event. It does not refer to an event, which hypothetically might have caused death, if it were more severe.
- Requires hospitalization or prolongation of an existing hospitalization.
 - > The following hospitalizations will **not** be considered serious:
 - Preplanned (before study) hospital admissions, unless the hospitalization is prolonged.
 - Planned admissions (as part of the study, e.g. routine biopsies).
 - Re-hospitalizations lasting less than 24 hours.
 - Emergency room visits.
 - Hospitalizations for elective surgery for a pre-existing condition. If untoward event occurs during an elective procedure, its occurrence must be reported as an AE, either serious or non-serious, according to the usual criteria.
- Results in persistent or significant disability/incapacity
 - The term disability means a substantial disruption of a person's ability to conduct normal life functions. This definition is not intended to include experiences of relatively minor medical significance, such as uncomplicated headache, nausea, vomiting, diarrhea, influenza, and accidental trauma (e.g., sprained ankle) which may interfere or prevent everyday life functions but do not constitute a substantial disruption.
- Is a congenital anomaly/birth defect.

CONFIDENTIAL

Any medically significant events that may require medical or surgical intervention to prevent one of the outcomes listed above.

11.1.1 Serious adverse event collection and reporting

It is the Investigators responsibility to report all SAEs (including all secondary efficacy outcomes) that occur from signing of informed consent and randomization through Day +37 by entering serious adverse events data into the InformTM EDC system within 24 hours of becoming aware of the SAE; the SAE must be followed through resolution or stabilization.

• Consented patients that withdraw from the study **prior** to randomization and experiences an SAE, the event must be followed (data collection) through the completion of the screening Encounter 1 or 2 and the completion of the screening eligibility eCRF.

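### The MI definition lets an index PCI serve as the only supporting feature, so a marker rise and fall after the qualifying procedure counts as an MI without symptoms or ECG change

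*Combined protocol and SAP*

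**What the plan says.** - **MI definition (5.10.3).** Troponin or CK-MB must show a rise and fall "of biochemical markers of myocardial necrosis to at least twice the upper limit of the normal range, with at least one of the following". Four features follow: ischemic symptoms, pathologic Q-waves, ischemic ECG changes, and "coronary artery intervention (*e.g.*, coronary angioplasty". Any one is enough. Nothing separates the index procedure from a later, unplanned intervention.
- **Index procedures (5.3.1).** The minor list includes "cardiac catheterization (with or without percutaneous coronary intervention".
- **Exclusions (5.2.2).** The cardiac exclusion is "cardiac surgery (*e.g.*, coronary artery bypass, heart valve replacement". PCI is not named.
- **PCI patients are expected (7.1).** The antiplatelet policy is justified partly on their account: "Antiplatelet drugs are also standard of care for some procedures, such as percutaneous coronary interventions".
- **Event window (5.12).** Events count when they occur "between the day of warfarin discontinuation (Day -5) and 30 to 37 days after the day of the surgery/procedure", so Day 0 is inside the window.
- **Adjudication (9.6).** The event committee provides "independent and blinded adjudication of the primary efficacy and safety outcomes as well as all cause deaths". MI is not in that remit.
- **SAE reporting (11.1.1).** Investigators must "report all SAEs (including all secondary efficacy outcomes" within 24 hours of becoming aware of them.
- **Analysis (5.12.3).** MI is compared with Fisher's mid-p test.

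**The concern.** A supporting feature is there to show that a marker change reflects a clinical ischemic event. For a patient enrolled for PCI, the fourth feature is present on Day 0 because of the reason for enrollment. The definition then reduces to its biomarker half.

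The plan deals with this problem elsewhere. Section 5.10.2 removes expected intra-operative bleeding and hemodilution from major bleeding, and 5.10.1 requires that systemic embolism have no other likely mechanism. The MI definition has no counterpart.

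What is at stake is how far the MI result can be interpreted. The protocol schedules no troponin or CK-MB testing, so the number of index-procedure events would depend on which sites measure serial markers after PCI. The reported MI rate would partly reflect local testing habits, and the comparison between arms would be less precise. Each such event would also be entered as an SAE.

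**Working it through.** **Reading the sections together.** No stated sample size, power or alpha rests on the MI definition, so there is no plan figure to reproduce. The check is whether any rule stops an index PCI from supplying the feature.

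1. Can an index-PCI patient be enrolled? Yes: 5.3.1 lists the procedure, 5.2.2 does not exclude it, and 7.1 expects it.
2. Is Day 0 in the event window? Yes (5.12).
3. Does the fourth feature exclude the index procedure? No (5.10.3).
4. Is a second feature, or a higher marker threshold after PCI, required? No (5.10.3).
5. Would a later step reclassify the event? None is described; 9.6 does not list MI.

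A marker rise and fall to at least twice the upper limit after an index PCI therefore meets the definition on its literal terms.

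**Illustration of size.** Inputs:

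- Patients per arm: 1,813 (synopsis and section 2.0).
- Test: two-sided Fisher's mid-p at 0.05. The test is from 5.12.3; 5.12.3 gives no alpha, so 0.05 is assumed.
- Share of patients with an index PCI: assumed 2% to 5%.
- Share of those with a qualifying marker rise and fall: assumed 10% to 30%.
- True MI rates apart from these events: assumed 2% vs 1%.

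The index-procedure event rate per arm is q = PCI share × marker share:

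- 2% × 10% = 0.2%
- 3% × 10% = 0.3%
- 3% × 30% = 0.9%
- 5% × 30% = 1.5%

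The observed rates become 2% + q and 1% + q. The risk difference stays at 1 percentage point. Its standard error is √{[p₁(1−p₁) + p₂(1−p₂)] / 1,813}, and the ratio is (2% + q)/(1% + q). Power is the exact probability of mid-p ≤ 0.05, summed over the two binomial distributions.

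| q per arm | Events per arm (1,813 × q) | Ratio | SE of difference (percentage points) | Mid-p power |
|---|---|---|---|---|
| 0 | 0 | 2.00 | 0.40 | 70% |
| 0.2% | 3.6 | 1.83 | 0.43 | 64% |
| 0.3% | 5.4 | 1.77 | 0.44 | 62% |
| 0.9% | 16.3 | 1.53 | 0.51 | 50% |
| 1.5% | 27.2 | 1.40 | 0.57 | 42% |

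For example, at q = 0 the standard error is √[(0.0196 + 0.0099)/1,813] = 0.40 points. At q = 1.5% it is √[(0.033775 + 0.024375)/1,813] = 0.57 points.

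The pattern does not depend on that contrast. With assumed true rates of 1.0% vs 0.5%, a PCI share of 1% to 5% and a marker share of 10% to 25%, q runs from 0.1% to 1.25% (about 2 to 23 patients per arm). Power then falls from 40.6% to between 36.8% and 18.5%.

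**The case against.** **The rule may be deliberate.** Section 5.10 says the secondary endpoints follow consensus criteria or criteria from earlier trials, and 5.10.3 cites a source for MI that cannot be consulted here. Counting marker-defined necrosis after a coronary intervention may have been intended. This stands to the extent that the events cannot be called false. A reader might infer that they are spurious infarctions, but the documents do not show that, and some may be true silent peri-procedural infarctions. The definition still does not say that index procedures were meant to count.

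**The biomarker criterion is demanding.** A reader might infer that any raised troponin after an index PCI becomes an MI. It does not: serial values showing a rise and fall are needed, the level must reach twice the upper limit, and no marker testing is scheduled. This limits how often the problem arises and makes it depend on local practice.

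**The comparison stays fair.** A reader might infer that the extra events bias the trial toward one arm. Nothing supports that. Treatment is double-blind (5.1), randomization is stratified by site (5.5.2), and equal additive events leave the expected risk difference unchanged. The loss is in precision, and the ratio moves toward 1.

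**MI carries little weight in the design.** It is listed first among the secondary efficacy endpoints, but no hierarchy is stated. It has no power target, no stopping role in 5.12.5 and no part in the non-inferiority conclusion. This stands, and it keeps the point minor.

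**Conclusion.** The point holds as a minor flaw in an endpoint definition. On the plan's own wording, the entry procedure can supply the only supporting feature for MI, and no described step corrects it. The consequence is a higher absolute MI rate that depends on local marker testing, a less precise comparison and a ratio closer to 1. There is no directional bias, and ATE and major bleeding are untouched.

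The size is uncertain. The PCI share, the marker-rise rate and the MI rates are all assumptions. Across the main range shown, power for an assumed 2% vs 1% contrast drops from 70% by about 6 points at the low end (to 64%) and 28 points at the high end (to 42%). If few patients have an index PCI, or few sites measure serial markers, the effect is small.

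**What to change.** In 5.10.3, state that the index coronary intervention does not by itself count as the supporting feature. A marker rise and fall after an index PCI then counts as an MI only with ischemic symptoms, pathologic Q-waves or ischemic ECG changes, which are the other three features already listed. Report events after an index PCI that meet only the marker criterion in a separate line by arm.

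The cost is a sentence or two in 5.10.3, matching eCRF guidance and one extra table row. No tests, visits or changes in care are needed. The downside is that some true but silent peri-procedural infarctions leave the MI count; the separate line keeps them visible.

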5.10.4 Secondary bleeding endpoint

Minor bleeding

 symptomatic or clinically-overt bleeding that does not satisfy the criteria for major bleeding

5.10.5 Procedures and interventions after an efficacy or bleeding outcome

In patients who develop a non-fatal efficacy or bleeding outcome, **standard treatment in accordance with usual clinical practice will be provided.** If the efficacy or bleeding outcome occurs during treatment with study drug, the local investigator can temporarily or permanently discontinue study drug, depending on the patient circumstances, although blinding to treatment allocation will be maintained.

If the efficacy or bleeding outcome requires unblinding to treatment allocation, as this may impact on patient treatment, the local investigator must contact the Principal Investigator (PI) or designee of BRIDGE to discuss the clinical details of the case. The PI or designee will make the ultimate decision to maintain the blind or unblind. If unblinding is determined necessary, the local

CONFIDENTIAL

investigator will have to utilize the unblinding module in the IXRS randomization system (internet or telephone) to complete the process. Once unblinding has occurred, the patient will not be eligible for further drug assignments. (Refer to Sections 7.0 Potential Co-Interventions)

All patients who develop a non-fatal efficacy or bleeding outcome will complete follow-up until the end-of-study assessment, between Day +30 to Day +37 and any subsequent efficacy and bleeding outcomes will be documented.

5.11 Sample Size Determination and Feasibility

5.11.1 Assumptions for sample size determination

This trial seeks to show that not administering bridging anticoagulation is not inferior to administering bridging anticoagulation in patients with atrial fibrillation or atrial flutter who require temporary interruption of warfarin. The non-inferiority analysis strategy combines tests for equivalence and for superiority of the placebo arm. Superiority of the placebo arm is plausible as bridging therapy may cause excessive major bleeding that would require prolonged interruption of warfarin therapy and, consequently, an extended period of time at an increased risk for ATE. The power of a given trial design to detect non-inferiority depends on the margin of clinically meaningful difference between the two treatment strategies (bridging vs. no bridging), the sample size of the two arms, and the anticipated rates of ATE in the two arms. The sample size estimates are based on the following assumptions:

- incidence of ATE in bridging group = 1.0% (derived from systematic reviews of patients with atrial fibrillation or atrial flutter who received bridging anticoagulation)
- incidence of ATE in "no bridging" group = 1.0% (derived from linked administrative database and cohort study of patients with atrial fibrillation or atrial flutter who did not receive bridging)
- non-inferiority margin = 1.0% (defined as the outer bound of the 95% CI of an absolute rate of ATE above the bridging group)

5.11.2 Sample size determination

Based on the above assumptions regarding ATE incidence in the bridging and no bridging groups, the non-inferiority margin of 1.0%, power of 80%, and a 2-tailed alpha of 0.05, we will require *1,641 patients per arm*.

	Non-infe	eriority M	argin	
ATE in LMWH (Bridging) Arm	0.5%	1.0%	1.5%	2.0%
0.5%	3308	927	465	307
1.0%	6317 <	1641	772	454
1.5%	9344	2375	1088	625
2.0%	12373	3127	1412	814

We also hypothesize that placebo has superior bleeding rates compared to LMWH based on the following assumptions: i) incidence of major bleeding in bridging group is 3.0%; and ii) incidence of major bleeding in no bridging group is less than the bridging group. If we assume that the incidence of major bleeding is ~3.0% for the LMWH group, as derived from our background work, 1.0% in the placebo group (as derived from trials where patients received warfarin alone after surgery [27]), and a 2-tailed alpha of 0.05, the proposed trial (with 1,641 patients per arm) has 98.8% power to detect superiority for the bleeding endpoint. The figures represent the required sample size per group, based on a power of 80%, and a 2-tailed alpha of 0.05, to detect differences in various incidences of major bleeding between the bridging group and "no bridging" group.

Bleedin	ng in Pla	cebo (No E	Bridging) Arm
0.5%	1.0%	1.5%	2.0%
769	2237	11194	
486	1138	3028	14209
344	772	1488	3788
262	508	914	1828
209	384	640	1113
	0.5% 769 486 344 262	0.5%1.0%76922374861138344772262508	769223711194486113830283447721488262508914

5.12 Statistical Analysis of Endpoints

The analysis of study endpoints is based on events which occurred between the day of warfarin discontinuation (Day -5) and 30 to 37 days after the day of the surgery/procedure (Day +30 to Day +37).

If a patient has the surgery/procedure delayed for ≤ 3 days, the final day of follow-up will be 30 to 37 days after the rescheduled surgery/procedure date (i.e., Day +30 to +37 after new Day 0). If a patient has the surgery/procedure delayed for >3 days or cancelled and study drug is no longer administered, the final day of follow-up will be 30 to 37 days after the originally scheduled surgery/procedure date (i.e., Day +30 to +37 after original Day 0). If follow-up data is not available for the specified time points and the patient is alive, the patient will be considered missing for the primary endpoints.

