5.12.1 Primary efficacy endpoint analysis

The primary efficacy outcome is ATE, defined by one or more of the following events occurring within the time period specified above:

- ischemic stroke
- transient ischemic attack
- systemic embolism

If the patient dies before day 35 and has not had the primary event, then it will be assumed that the patient would not have had an event had he/she been followed for 35 days.

The primary endpoint analysis is a non-inferiority analysis with an absolute margin of 1.0 percent. For that reason, the statistical test must provide confidence limits for the difference in rates. The two tests available with standard software that provide corresponding confidence limits are the likelihood ratio test and Barnard's test. The likelihood ratio test does not maintain the nominal alpha level for small sample sizes, and so that test will not be used.

There is a proposed an unconditional exact test based on a minimax elimination of the nuisance parameter [38]. The reference set was defined to be the set of all 2 x 2 tables with fixed row margins and all possible column margins. The test and its associated 95 percent confidence limits will be calculated using the StatXact 7 software [39]. If the upper 95 percent confidence limit for the difference in event rates (placebo primary event rate - bridging anticoagulation primary event rate) is less than 0.01, then the primary endpoint will have been met for placebo.

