5.12.6 Sensitivity analyses

We expect that with good study conduct and an appropriate patient population, the number of patients with missing data will be small. As a sensitivity analysis, we will evaluate the primary and secondary study endpoints based on time to an endpoint event. In the sensitivity analysis, patients who have incomplete follow-up will be censored at the date of last contact. For the primary efficacy outcome of ATE, if a patient dies before day 35 and has not had the primary event, then the patient will be censored on the date of death.

This is a sensitivity analysis because the evidence used to estimate the anticipated event frequency and define the non-inferiority margin (section 5.11) is expressed as an event rate at a fixed time (35 days), as opposed to a hazard function. Although it is possible to assess non-inferiority using censored data, analysis of binary outcomes remains appropriate for instances where the amount of censoring is very low. [43]

To evaluate the properties of the two analysis strategies, consider an exponential distribution censored so that the overall event rate approximates 1 percent. Based upon 1,000,000 simulations assuming 1641 patients per arm and no losses to follow-up, the observed alpha level for the log-rank test is approximately 0.0452, and the alpha level for Fisher's mid-p is approximately 0.0481 (for a nominal alpha level of 0.05). Both tests are affected by the small number of events, but the log-rank test is affected slightly more. Assuming a hazard ratio of 0.5 and testing for superiority, the power for the log-rank test was 51.98 percent whereas the mid-p test has a power of 52.76 percent. Although it is difficult to generalize from these two simulations, we anticipate that the log-rank test is, if anything, conservative for small numbers of events. Further, the log-rank test has slightly less power to detect differences than Fisher's mid-p test (because of its conservativeness), but the difference in power shrinks as the fraction of patients with partial follow-up expands.

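### Section 5.12 would class a patient with a recorded ATE or major bleed as missing if later follow-up is absent; the rule should say that a recorded event counts

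*Combined protocol and SAP*

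**What the plan says.** All references are to the combined protocol and SAP.

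- **Section 5.12** opens with "The analysis of study endpoints is based on events which occurred between the day of warfarin discontinuation (Day -5") and the end of follow-up at Day +30 to Day +37. It closes with the missing-data rule: "If follow-up data is not available for the specified time points and the patient is alive, the patient will be considered missing", and applies this to the primary endpoints, so to ATE and major bleeding alike.
- **Section 5.10** says all endpoints are analysed in the MITT population, which is every patient whose warfarin was discontinued.
- **Section 5.12.1** treats a patient who "dies before day 35 and has not had the primary event, then it will be assumed that the patient would not have had an event" as a non-event for ATE. Its horizon is 35 days, while section 5.12 uses Day +30 to +37 and section 5.10 counts at least 36 days.
- **Section 5.10.5** says patients with a non-fatal outcome event "will complete follow-up until the end-of-study assessment". **Section 13.1** allows withdrawal at any time.
- **Section 5.12.6** adds a time-to-event sensitivity analysis in which "patients who have incomplete follow-up will be censored at the date of last contact". Deaths without ATE are censored at death.

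**The concern.** The missing-data rule asks two things: is the patient alive, and are there data at the specified time points? It does not ask whether the endpoint has already happened. Take a patient with an adjudicated stroke on Day +3 who then withdraws and has no Day +30 to +37 contact. Under the rule as written, that patient is missing and the stroke is not analysed. Under the opening sentence of the same section, the stroke is an event in the window and counts. Two statisticians could code this patient differently, each with a sentence of the plan in support.

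This matters most for ATE. The primary analysis is a non-inferiority test on a rare endpoint. If events are dropped in equal proportion from both arms while the denominators barely change, the difference shrinks towards zero and non-inferiority is easier to claim. For major bleeding the comparison is for superiority, so equal dropping weakens the contrast.

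**Working it through.** **Inputs.** From sections 5.11.1, 5.11.2 and 5.12.1: ATE 1.0% in each arm ("incidence of ATE in bridging group = 1.0"%, and the same for no bridging), margin 1.0%, 80% power, 2-tailed alpha 0.05, 1,641 per arm required, and success if the upper 95% limit for placebo minus bridging is below 0.01. From the synopsis: 1,813 per arm planned. The plan gives no rate of loss to follow-up; section 5.12.6 says only that missing data should be few. The loss rates below are therefore **assumptions**.

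**The plan's own figure.** The simple formula gives (1.960 + 0.842)² × 2 × 0.01 × 0.99 / 0.01² ≈ 1,555. Exact binomial enumeration of the likelihood-ratio test gives 80.3% power at 1,641, the first n to reach 80%, so the stated 1,641 reproduces. Expected ATEs per arm are 1,641 × 0.01 = 16.4, or 1,813 × 0.01 = 18.1.

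**Effect at the boundary.** Score test against the margin: z = (p̂P − p̂B − 0.01) / √[p̃P(1 − p̃P)/nP + p̃B(1 − p̃B)/nB], where p̃ are the estimates constrained to differ by 0.01. Non-inferiority needs z < −1.960. A score-ordered unconditional exact test, used as a stand-in for the StatXact procedure, gave the same pass/fail boundaries.

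- 20/1,641 vs 16/1,641: difference 0.00244; p̃ = 0.01747 and 0.00747; standard error 0.00387; z = (0.00244 − 0.01)/0.00387 = −1.954. Upper limit 1.002%: fails.
- One of the 20 set to missing, 19/1,640 vs 16/1,641: difference 0.00183; p̃ = 0.01731 and 0.00731; standard error 0.00385; z = −2.12. Upper limit 0.93%: passes.
- Expected result, 16 vs 16 at 1,641: upper limit 0.71%. Non-inferiority holds up to 19 placebo events, so four more are needed to fail.
- At 1,813 per arm, 18 vs 18 gives 0.68%. It fails at 23 (1.005%), and 22/1,812 passes (0.94%).

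**Effect on the false non-inferiority rate.** Let true rates be 2.0% placebo and 1.0% bridging, and let shares lP and lB of ATE patients be lost and dropped. The analysed rates become about 2.0% × (1 − lP) and 1.0% × (1 − lB). The denominators are left unchanged, since only a few patients are removed. The chance of passing is the sum of the two binomial probabilities over all passing tables, with 1,641 per arm.

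| Assumed loss of ATE patients | Analysed difference | P(non-inferiority) |
|---|---|---|
| none | 2.00 − 1.00 = 1.00% | 2.4% |
| 2% both arms | 1.96 − 0.98 = 0.98% | 2.7% |
| 5% both arms | 1.90 − 0.95 = 0.95% | 3.1% |
| 10% both arms | 1.80 − 0.90 = 0.90% | 4.0% |
| 10% placebo only | 1.80 − 1.00 = 0.80% | 6.6% |
| 10% bridging only | 2.00 − 0.90 = 1.10% | 1.3% |

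At 1,813 per arm the first four rows are 2.4%, 2.7%, 3.2% and 4.2%. At the design rate of 1.0%, the number of placebo events dropped is small: 16.4 × 0.02 = 0.3, 16.4 × 0.05 = 0.8, 16.4 × 0.10 = 1.6.

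**The case against.** The best defence is that the rule was never meant to reach these patients. Section 5.12 analyses events that occurred in the window, section 5.12.1 defines ATE by events in that window, and the death rule first asks whether the event has happened. On that reading, missing means unknown status. The reading is reasonable, but the sentence does not say it, and its literal sense is the opposite.

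Second, such patients should be few. Section 5.8 requires primary outcomes to be documented within 24 hours of knowledge, contact is at least weekly, the last encounter may be by telephone, and section 5.10.5 expects full follow-up after an event. This limits the size of the problem. It is not an analysis rule, and withdrawal remains possible.

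Third, the time-to-event analysis in section 5.12.6 keeps an event that precedes loss, and keeps partial follow-up. That is correct and covers much of the ground. But it is a sensitivity analysis, it refers to the log-rank test, and it states no confidence limit against the 1.0% margin, so it cannot replace the primary decision.

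A reader might also infer three stronger points that the documents do not support:

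- **That event-free deaths drop out.** They stay in the denominator as ATE non-events ("it will be assumed that the patient would not have had an event had he/she been followed for 35 days"), and a patient with an ATE who later dies is not removed. Fatal bleeding is itself a major bleed, and death is a separate secondary endpoint. Wanting ATE-or-death tested on a margin set for ATE is a preference.
- **That one event decides the trial.** This is so only at the boundary. With 1.0% in both arms, 5.3% of trials at 1,641 per arm would land where one dropped placebo event turns a fail into a pass, and there non-inferiority would be true.
- **That the gap between 1,813 and 1,641 shows how many patients may be lost.** The documents do not explain the gap.

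**Conclusion.** The point holds as a defect in a stated rule. Taken literally, section 5.12 discards recorded primary events and contradicts both its own opening and the MITT definition in section 5.10.

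The likely numerical effect is modest: false non-inferiority rises from 2.4% to between 2.7% and 4.0% for assumed losses of 2% to 10% of ATE patients in both arms. The direction depends on who is lost: placebo-only loss of 10% gives 6.6%, bridging-only loss 1.3%. Nothing in a double-blind trial makes one-sided loss the expected case.

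These figures assume that the loss falls on ATE patients over and above any loss among event-free patients. If both groups were lost at the same rate, numerator and denominator would shrink together and the rates would not be biased; only precision would suffer. The boundary results rest on score limits, and the StatXact procedure could shift them slightly.

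**What to change.** Replace the missing-data sentence in section 5.12 with wording such as:

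> A patient with an adjudicated ATE (or major bleed) in the window counts as having that event regardless of later follow-up. Only living patients without that event whose status to Day +30 is unknown are missing for that endpoint.

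In the same edit, align day 35 in sections 5.12.1 and 5.12.6 with the Day +30 to +37 window, and state the day from which it is counted.

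Optional and supportive only: a tipping-point analysis that varies the ATE rate among the missing patients and reports the upper limit against the 1.0% margin. It is useful because the reworded rule still leaves out event-free patients of unknown status, which nudges both observed rates upwards.

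The cost is a wording change and, if wanted, one extra table. No new data are needed, since events are already recorded and adjudicated blind (section 9.6). The change should be made before unblinding, because afterwards either reading could look chosen for its result.
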